7.9.1.2 Analysis of Key Secondary Endpoints

7.9.1.2.1 Hypothesis

For key secondary endpoint of return to work, the following hypothesis will be tested:

$$H_0: S_A(t) = S_C(t)$$

$$H_a: S_A(t) \neq S_C(t)$$

Where $S_A(t)$ and $S_C(t)$ are the survival functions for freedom from return to work for the VenaSeal™ system arm and ETA or surgical stripping arm, respectively.

For the other key secondary endpoint of primary target vein closure rate at 6 months, the following hypothesis will be tested:

$$H_0: S_A(t) \leq S_C(t) - 10\%$$

$$H_a: S_A(t) > S_C(t) - 10\%$$

Where $t = 6$ months, and $S_A(t)$ and $S_C(t)$ are the survival functions for freedom from vessel re-opening at 6 months in the VenaSeal™ system arm and the ETA or surgical stripping arm, respectively and -10% is the non-inferiority margin.

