7.9.1.2.4 Analysis Methods

For the return to work endpoint, a Kaplan-Meier survival estimator will be used to estimate the survival functions for both the VenaSeal™ and the control arm (i.e., ETA or Surgical Stripping). Day zero is the date of the index procedure. The censoring time is the time to study exit, the later of either the last contact date or the discontinuation date, or the time point for analysis, whichever comes first. A cumulative incidence figure will be produced to compare the two treatments. A log-rank test will be used to test whether the survival distributions differ between the treatment groups. If a patient is reported to have returned to work, but the date of return is unknown, the return date will be imputed from the date of the follow-up visit. For those who have returned to work, the median, Q1, Q3, minimum, and maximum will summarize the number of days to return to work, as well as the number who have not returned to work in each treatment arm.

The treatment effect for primary target vein closure at 6 months, one of the key secondary endpoints, is the difference in the survival curves at time t for each randomized study. A Kaplan-Meier survival estimator will be used to estimate each curve. Day zero is the date of the index procedure. The censoring time is the time to last study visit (scheduled or unscheduled), the time point for analysis, or time to exit, whichever comes first. The non-inferiority test for treatment (VenaSeal) versus control (ETA or Surgical Stripping) will be performed using the test statistic proposed in da Silva, Logan and Klein (2009)³. The Z test statistic will calculate $S_A(t) - S_C(t) + 0.10$ for the numerator where t is at 6 months and the square root of the sum of the Greenwood's variance estimators for each of $S_A(t)$ and $S_C(t)$ in the denominator.

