The rate of reintervention will be summarized by treatment arm in each study. The rate is calculated such that the numerator is the number of reinterventions and the denominator is the number of vein-years of follow-up. The amount of follow-up per person is defined as their date of exit or last known follow-up minus their date of index procedure. The vein-years is the amount of person-years times the number of target veins. A Poisson model will compare the rate of reintervention between treatment arms, using the number of reinterventions as the outcome and the person years of follow-up as an offset.

Determination of Subjects for Analysis

The reintervention analysis will consist of the ITT population.

5. Time to reintervention of any target vein (including primary target vein) through 60 months, as measured by the time between the index procedure and the first reintervention procedure. Subjects enrolled in the VenaSeal vs. Surgical Stripping Study will be followed through the 12 months visit only.

Hypothesis

The following hypothesis will be tested:

$H_0: S_A(t) = S_C(t)$

$H_a: S_A(t) \neq S_C(t)$

where $S_A(t)$ and $S_C(t)$ are the survival function estimates at time point t in the VenaSeal™ system arm and the ETA or surgical stripping arm, respectively. In the VenaSeal vs. Surgical Stripping Study, $t=12$ months and is otherwise $t=60$ months.

Endpoint Definition

A reintervention is a retreatment of any segment of any target vein in the target limb previously treated as part of the study at the index procedure.

Analysis Methods

The time to reintervention will be summarized by treatment arm in each study. Time to the first reintervention of any target vein by treatment will be presented with Kaplan-Meier estimation. Day zero is the date of the index procedure. The censoring time is the time to study exit, the later of either the last

contact date or the discontinuation date, or the time point for analysis, whichever comes first. A log-rank test will be used to compare arms.

Determination of Subjects for Analysis

The reintervention analysis will consist of the ITT population.

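### Time to reintervention: the null hypothesis is stated at one time point (60 or 12 months), but the only test named is a log-rank test of the whole curve, so the p-value does not test the stated hypothesis

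*SAP*

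**What the plan says.** Item 5 of SAP 7.9.1.4 defines the endpoint as time from index procedure to first reintervention of any target vein, and gives H0: S_A(t) = S_C(t) against a two-sided alternative. The two quantities "are the survival function estimates at time point t in the VenaSeal™ system arm" and the comparator arm. The time point is then fixed: "In the VenaSeal vs. Surgical Stripping Study, $t=12$ months and is otherwise $t=60$ months".

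On analysis, "Time to the first reintervention of any target vein by treatment will be presented with Kaplan-Meier estimation". Follow-up is censored at study exit, meaning the later of the last "contact date or the discontinuation date, or the time point for analysis, whichever comes first". The comparison is one sentence: "A log-rank test will be used to compare arms". No fixed-time test is given for this endpoint.

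Elsewhere the SAP matches hypothesis to test:

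- **Return to work (7.9.1.2.1, 7.9.1.2.4).** S_A(t) and S_C(t) "are the survival functions for freedom from return to work for the VenaSeal™ system arm and ETA or surgical stripping arm, respectively", with no fixed t, and the test is log-rank. Return to normal activities (7.9.1.7, item 1) follows the same pattern.
- **Closure at 6 months (7.9.1.2.1, 7.9.1.2.4).** The hypothesis is fixed at t = 6 months. The test is a Z statistic on the Kaplan-Meier difference at 6 months, with "the square root of the sum of the Greenwood's variance estimators" in the denominator.

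**The concern.** Equality at t and equality of the curves up to t are different hypotheses. Two arms can have the same freedom from reintervention at 60 months with different timing; the stated null is then true and the log-rank null false. Curves that cross can differ at 60 months while early and late contributions partly cancel in the log-rank sum.

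Attrition widens the gap. The log-rank statistic counts observed events, and late events are lost to dropout more often than early ones. The Kaplan-Meier estimate at t corrects for this when censoring is non-informative.

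What is at stake is the wording of a conclusion. With a hypothesis fixed at 60 months and one p-value beside it, a reader will take the p-value as evidence about 60 months. Item 4 does not fill the gap: its Poisson model compares rates over all follow-up.

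The hypothesis is also worded about estimates, whereas a null should concern the true survival functions.

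**Working it through.** **No stated figure to reproduce.** The documents give no event rate, event count, alpha or power for this endpoint.

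**Inputs from the documents.** About 264 subjects in the ETA study and 108 in the stripping study (SAP 5.1), randomized 1:1 (protocol 10.4), so 132 and 54 per arm. Horizons are 60 and 12 months (SAP 7.9.1.4, item 5).

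**Assumptions.** Two-sided 5% level, reintervention by month 60 of 5-20%, event times uniform within stated windows, and 40% attrition spread uniformly over 0-60 months. Attrition and censoring are the same in both arms.

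**Direct calculation, extreme pattern.** Both arms have 20% reintervention by month 60, so the stated null is true. Arm A's events fall in months 0-12 and arm C's in months 36-60.

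1. True events per arm: 132 × 0.20 = 26.4.
2. Dropout at the mean event time: A, 40% × 6/60 = 4%; C, 40% × 48/60 = 32%.
3. Observed events: A, 26.4 × 0.96 = 25.3; C, 26.4 × 0.68 = 18.0; total 43.3.
4. Under the log-rank null, A's expected share at each event is S_A/(S_A + S_C), because equal censoring cancels. It falls from 0.500 to 0.8/1.8 = 0.444 and returns to 0.500, averaging 0.472.
5. E = 43.3 × 0.472 = 20.4; V ≈ 43.3 × 0.472 × 0.528 = 10.8.
6. Z is centred at (25.3 − 20.4)/√10.8 = 1.49.
7. Rejection = Φ(1.49 − 1.96) + Φ(−1.96 − 1.49) ≈ 0.32.

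Without dropout, 26.4 events are observed in each arm. E = 52.8 × 0.472 = 24.9, V = 13.1, Z = 1.5/3.6 = 0.4 and rejection is about 7%. Most of the excess therefore comes from attrition.

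**Same calculation, overlapping timing.** A's events fall in months 0-12 and C's in months 0-36. C's dropout at its mean event time is 40% × 18/60 = 12%, so C has 26.4 × 0.88 = 23.2 observed events. The mean share is 0.481, E = 48.6 × 0.481 = 23.4 and V = 12.1. Z = (25.3 − 23.4)/3.48, about 0.56, and rejection is about 9%.

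**Simulation** (132 per arm, equal 60-month rates, 40% attrition; 1,000 to 4,000 runs per cell, ranges over repeated runs). Log-rank rejection by reintervention rate:

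| Timing, months (A vs C) | 5% | 10% | 15% | 20% |
|---|---|---|---|---|
| 0-12 vs 36-60 | 6-9% | 15-17% | 22-23% | 31-33% |
| 0-12 vs 0-60 | – | – | 12% | 14-15% |
| 0-12 vs 0-36 | 4.8% | 6.1% | 7.4% | 9.0% |

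For 0-36 vs 0-60 the range is 5.6-7.3%. With 20% attrition, the first row becomes 8-9%, 11-13% and 15-16% at 10, 15 and 20% reintervention. The Kaplan-Meier/Greenwood Z at 60 months stays at 4-7% in the patterns where it was run. A still later window (0-12 vs 48-60) with exponential dropout gives, at 60-month freedom of 0.80, log-rank rejection of 7.3, 10.7, 26.0 and 54.1% for 0, 10, 30 and 50% dropout.

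**When the 60-month rates do differ** (10% early vs 20% late, 40% attrition), log-rank power is 15% against 47-51% for the fixed-time test. With 0-12 vs 0-36 timing the gap is about 16 points; with identical timing it is about 1.

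**Proportional hazards.** Null rejection is 4.9-5.2% for log-rank and 5.4-5.5% for the fixed-time test. Power for 0.90 vs 0.80 at 30% dropout is 55.5% for each.

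**Stripping study** (54 per arm, 12 months, events in months 0-3 vs 9-12, 12-month freedom 0.80-0.95, dropout 0-10%). Log-rank rejection is 4-7%.

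**The case against.** The best defence is that the fault lies in one clause and the test is right. Protocol 5.2.3 and the SAP both name the endpoint as time to reintervention through 60 months, which is a whole-curve endpoint, and log-rank is the standard test for it. If one arm's reinterventions come early and the other's late, time to reintervention really differs, and rejecting is correct for that endpoint. This stands, and it is why the test should be kept and the hypothesis reworded.

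The extreme pattern is also unlikely on the documents' own evidence. Protocol 4.1 reports that the five-year extension of the pivotal device-versus-RFA trial saw no new failures between 36 and 60 months in either group. That outcome is recanalization rather than reintervention, but it argues against many late events. On attrition, protocol 6.2 says only that it may be higher at 48 and 60 months, gives no rate, and permits remote visits to limit it.

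A reader might infer that log-rank is invalid here and should be replaced, or that the trial carries a 15-33% false-positive rate. The documents support neither. The test is valid for equality of the curves, and those percentages are errors only against the literal single-time wording, under assumed timing and attrition.

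What the defence does not remove is that the SAP poses a 60- or 12-month question and names no test that answers it.

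**Conclusion.** The mismatch is real and visible within item 5. As written, the log-rank p-value does not test the stated hypothesis.

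Its size is conditional. In the ETA study with equal 60-month rates and 40% attrition, log-rank rejection is about 5-9% for moderate overlap and 12-15% for early versus evenly spread events at 15-20% reintervention. It is about 15-33% at 10-20% reintervention only when one arm's events are all early and the other's all late; later events and heavier dropout raise it further. It is negligible under proportional hazards and in the stripping study at the rates tried. All event rates, timings and attrition levels are assumptions.

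A reader might also infer that a confirmatory conclusion is at risk. It is not: the endpoint lies outside the Hochberg procedure in SAP 7.5, and SAP 7.9.1.3 requires reports to state that such p-values are unadjusted. What depends on the fix is whether the trial can support a statement about a 60- or 12-month difference in reintervention.

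**What to change.** In SAP 7.9.1.4, item 5:

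1. Word the null for the log-rank test as equality of the true survival functions for all times through 60 months (12 months in the stripping study), on the model of return to work. Remove the reference to estimates.
2. Add the Kaplan-Meier difference S_A(t) − S_C(t) at t = 60 (12) months, with its Greenwood standard error and 95% CI. This is the closure statistic in 7.9.1.2.4 without the 0.10 margin.
3. State that only the quantity in step 2 supports any conclusion about a 60- or 12-month difference, and that the log-rank p-value speaks to the curves as a whole.

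The cost is a few lines of SAP text and a statistic already specified for closure. The small downside is one more unadjusted secondary comparison to report. The protocol prescribes no test for this endpoint, so under SAP 7.12 this looks like an SAP edit without a protocol amendment.

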7.9.1.5 Safety secondary endpoints

1. Adverse events (AEs) occurring in the target limb, evaluated from index procedure through 12 months.

Hypothesis

There is no formal hypothesis test for this study objective.

Endpoint Definition

Adverse events occurring in the target limb defined as any of the following:

- Hypersensitivity to VenaSeal™ adhesive, defined as an allergic reaction to the VenaSeal™ adhesive. The presence of hypersensitivity is confirmed through adjudication. Relatedness to a study procedure and relatedness to the study device are defined.
- Phlebitis, defined as inflammatory reaction of a treated vein. The presence of phlebitis is confirmed through adjudication. Relatedness to a study procedure and relatedness to the study device are defined.
- Granuloma, defined as a grouping of macrophages. The presence of granuloma is confirmed through adjudication. Relatedness to a study procedure and relatedness to the study device are defined.
- Endovenous glue induced thrombosis (EGIT) or endovenous heat induced thrombosis (EHIT) for VenaSeal or Thermal Ablation, defined as extensions of a thrombus that extend from the treated vein into the deep venous system. The presence of a glue extension, thrombus extension, or combination glue/thrombus is confirmed through DUS visualization of the extension into the common femoral vein or popliteal vein from the target vein and extension length is specified.

CEC determination of the above events will be used for reporting.

Analysis Methods

Adverse events that are in any of the above enumerated categories will be characterized. Adverse events will be categorized per the specified definitions, and then summarized by study group.

Determination of Subjects for Analysis

The safety analysis will consist of the ITT population.

2. Additional events evaluated through 12 months:

- Symptomatic deep vein thrombosis (DVT) events

- Symptomatic Pulmonary embolism (PE)
- Serious adverse events (SAEs)

Hypothesis

There is no formal hypothesis test for this study objective.

Endpoint Definition

CEC determination of serious adverse events will be used for reporting. The MedDRA codes for Deep vein thrombosis and Pulmonary embolism will be used for reporting of DVT and PE adverse events.

Analysis Methods

The probability of experiencing an SAE through 12 months will be summarized by treatment arm in each study. The probability for each treatment arm will be estimated using the Kaplan-Meier method. Day zero is the date of the index procedure. The censoring time is the time to study exit, the later of either the last contact date or the discontinuation date, or the time point for analysis, whichever comes first. The DVT and PE events will be summarized by reporting the number of events of each type and the number of patients in which they occurred, by treatment arm. Additionally, summary statistics will report the proportion of SAEs. Numerator is the number of target limbs (or subjects) with an SAE through 12 months, denominator is the number of target limbs (or subjects).

Determination of Subjects for Analysis

The safety analysis will consist of the ITT population.

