In addition to the above industry-initiated studies, the Lake Washington Vascular VenaSeal™ Post-Market Evaluation (WAVES) study was a single-center multiple-investigator, single-arm prospective study investigating the use of the VenaSeal™ system in patients with symptomatic VRD. The study assessed the use of the VenaSeal™ system in GSVs (n=48), SSVs (n=8), and accessory saphenous veins (n=14).³¹ Diseased veins of up to 20 mm diameter were included. The WAVES protocol did not allow adjunctive tributary treatment at the time of the index procedure which were staged at 3 months post-index procedure.

There were 70 veins treated in 50 subjects. All primary target veins (48 GSV, 14 ASV, and 8 SSV) showed 100% closure using DUS at 7 days and 1 month. Complete closure at 3 months was achieved in 70 (99%) of the treated veins. By 3 months, the revised Venous Clinical Severity Score (rVCSS) (6.5 ± 2.4 at baseline to 1.8 ± 1.4 at 1 month and 3 month; p<0.001), Aberdeen Varicose Vein Questionnaire (AVVQ) (17.3 ± 7.9 at baseline to 8.9 ± 6.6 at 1 month and 6.5 ± 7.2 at 3 month; p<0.001), and the EQ VAS (84 ± 12 at baseline to 88.3 ± 8.7 at 1 month and 88.6 ± 10.6 at 3 month; p = 0.002) all showed statistical improvement between baseline and 1 month, and baseline and 3 month visits. The percentage of patients who required adjunctive treatments at three months was lower than had been predicted by the treating physicians (65% versus 96%, p=.0002).³² Procedural pain was mild with a Nominal Pain Rating (NPR) of 2.2 ± 1.8, and the mean time to return to work and normal activities was 0.2 ± 1.1 and 2.4 ± 4.1 days, respectively.

Phlebitis was the most common AE, occurring in the treatment area or side branches in 10 patients (20%), but resolving in all but one subject (2%) by one month. One patient developed body hives within the first week of the procedure which was resolved following antihistamine and steroid treatment, this was said to be consistent with a cyanoacrylate allergy. There were no DVTs or other SAEs. One patient had a thrombus extension at the seven-day DUS which was no longer evident at the one-month DUS. Between the 1-month and 3-month visits, there was one AE, knee bursitis in the treatment limb which was determined as unrelated to the procedure.³²

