No Procedure treatment outcome (CEAP 2-5)	Subject is randomized (considered enrolled) but withdraws from the study after randomization without any attempt to conduct the procedure (e.g. COVID-19 exclusion, subject withdrawal, etc.).
Per-Protocol (PP) (CEAP 2-6)	The ITT population excluding subjects that are not treated with the assigned treatment modality and/or have not met the inclusion/exclusion criteria.
Phlebectomy	Surgical procedure to remove small varicose veins through a series of small (1-3 cm) incisions in the leg along the GSV and its tributaries.
Phlebitis	Inflammation of a vein, the grading of the phlebitis are as follows and subject may have more than one grading: P1: Inflammation of truncal or epifascial vein post-treatment, with palpable and/or non-palpable (Superficial thrombophlebitis) areas. Located within the treatment zone. It is caused due to Damage to treated vein by prescribed treatment with and without thrombus. P2: Superficial thrombophlebitis in residual varicosities/tributaries. Located outside of treatment zone. It is caused due to thrombosis of draining varices or tributaries secondary to closure of truncal vein P3: Inflammation of cutaneous and subcutaneous tissue. Located within or outside of treatment zone and adjacent tissues. It is caused due to tissue reaction to treatment or hypersensitivity.
Point of Enrollment (CEAP 2-5)	Subjects will be considered enrolled from the moment of randomization.
Point of Enrollment (CEAP 6)	Subjects will be considered enrolled from the moment the first component of the VenaSeal™ delivery system enters the body.

Medtronic Business Restricted

CONFIDENTIAL

VENASEAL SPECTRUM Clinical Investigation Plan

MDT18034

Version 5.0

Page 150 of 164

Medtronic

Pre-Screen Failure	Patients that were identified for screening (consenting in the study) but were not consented in the study
Pre-Screening	The process of identifying patients for potential inclusion in the study, prior to obtaining informed consent from the patient.
Primary Target Vein	The primary target vein should be the saphenous vein (GSV, SSV, accessory saphenous veins) which at the investigator's discretion is most likely responsible for the greatest portion of the patient's symptoms or pathology. This vein will be treated first.
Reintervention	Retreatment of any segment of the target vein in the target limb previously treated as part of the study at the index procedure.

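### The SAP's phlebitis definition is narrower than the protocol's P1–P3 grading, so P2-only and P3-only subjects fall outside the named safety endpoint if the SAP is read literally

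*SAP*

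**What the plan says.** SAP 7.9.1.5 (randomized studies) lists phlebitis among the target-limb adverse events evaluated through 12 months and gives it this definition: "Phlebitis, defined as inflammatory reaction of a treated vein". SAP 7.9.2.4 repeats the wording for the VLU Study. Neither section mentions grades.

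SAP 7.9.1.5 has two rules for the count. On whose decision is reported: "CEC determination of the above events will be used for reporting". On classification: "Adverse events will be categorized per the specified definitions, and then summarized by study group". SAP 7.9.2.4 carries the same two rules, without the split by group. There is no formal hypothesis test for this endpoint.

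Protocol Appendix B defines the same term more widely: "Inflammation of a vein, the grading of the phlebitis are as follows and subject may have more than one grading". The three grades are:
- "P1: Inflammation of truncal or epifascial vein post-treatment", placed within the treatment zone and attributed to damage to the treated vein.
- "P2: Superficial thrombophlebitis in residual varicosities/tributaries. Located outside of treatment zone", attributed to thrombosis that follows closure of the truncal vein.
- "P3: Inflammation of cutaneous and subcutaneous tissue. Located within or outside of treatment zone and adjacent tissues", attributed to a tissue reaction to treatment or to hypersensitivity.

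Protocol section 13.1 says the CEC classifies safety endpoint events by the definitions in its Charter, which is a separate document.

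**The concern.** The protocol and the SAP give different case definitions for one named safety endpoint in all three studies. The SAP's is the narrower, and the SAP says its own definitions do the sorting. SAP section 3 states that the objectives come from the protocol. Neither the SAP's version history nor its text records or explains a narrower phlebitis definition.

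What is at stake is the meaning of the reported phlebitis rate. A treated-vein-only rate is not the protocol's endpoint. It is also not comparable with the 20% that protocol section 4.1 quotes from the single-centre post-market study (WAVES), which counted the treatment area and side branches together. A second gap concerns skin and soft-tissue reactions. The SAP's hypersensitivity endpoint covers only an allergic reaction to the adhesive, so a P3 reaction of another kind has no named endpoint to go to. Protocol section 11.2 names nonspecific inflammation of these tissues among the foreign body reactions possible with VenaSeal, so this is not a remote case.

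**Working it through.** **1. Definitions side by side.** Inputs: Appendix B for the grades; SAP 7.9.1.5 and 7.9.2.4 for the endpoint definitions.

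| Appendix B grade | Site | Meets SAP phlebitis (treated vein)? | Meets SAP hypersensitivity (allergic reaction to the adhesive)? |
|---|---|---|---|
| P1 | Truncal or epifascial vein, inside the treatment zone | Yes, in essence | Not by itself |
| P2 | Remaining varicose branches, outside the zone | No: not a treated vein | No |
| P3, allergic to the adhesive | Skin and tissue beneath | No: not a vein | Yes |
| P3, other tissue reaction | Skin and tissue beneath | No: not a vein | No |

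The last row fits neither named endpoint.

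**2. Who is left out.** Appendix B lets one subject hold several grades. A subject with P1 plus P2 or P3 still meets the SAP definition. Only subjects with P2 alone, P3 alone, or P2 and P3 without P1 are left out. Two of three grades is therefore not two thirds of subjects.

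**3. The only frequency in the documents.** Protocol section 4.1 (WAVES) reports 10 patients with phlebitis among 50 subjects: 10/50 = 20.0%, which matches the stated figure. The exact 95% confidence interval is 10.0% to 33.7%. The count is not split by site, so it cannot be divided into P1, P2 and P3.

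**4. Illustration only.** Let *f* be the share of affected subjects who have a treated-vein component. No value of *f* is given, and the 20% all-grade rate is itself an assumption for this trial. Then:
- rate under the SAP wording = 20% × *f*
- subjects counted = N × 20% × *f*

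The planned VenaSeal group sizes are 264/2 = 132 (ETA study), 108/2 = 54 (stripping study) and 125 (VLU Study).

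| *f* (assumed) | SAP-wording rate | of 132 | of 54 | of 125 |
|---|---|---|---|---|
| 1.00 | 20% | 26.4 | 10.8 | 25.0 |
| 0.75 | 15% | 19.8 | 8.1 | 18.75 |
| 0.50 | 10% | 13.2 | 5.4 | 12.5 |
| 0.25 | 5% | 6.6 | 2.7 | 6.25 |

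At *f* = 1 the wording changes nothing. The table shows how much the answer depends on *f*; it does not estimate the loss.

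**5. Where the events go otherwise.** Protocol section 12.3 makes every target-limb adverse event reportable. SAP 7.10 summarizes adverse events by treatment, System Organ Class and Preferred Term, and lists each one. P2 and P3 events therefore remain visible, but under MedDRA terms rather than as the protocol's graded phlebitis.

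**The case against.** The strongest reply is that the reported count is the CEC's determination, and the CEC follows its Charter. If the Charter uses P1–P3, adjudicated phlebitis may already include every grade, and the SAP line may be only a shortened gloss. This stands as a reason not to claim that events will be left out. It does not remove the defect. The SAP also says that events are sorted by the definitions it prints, so a P1–P3 Charter would contradict the SAP, and a treated-vein Charter would contradict the protocol.

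It is also fair to say that the protocol is not tidy: Appendix B opens with inflammation of a vein, which P3 does not satisfy. And the events stay in the general tables. Both points stand. The second limits the harm but does not restore the named endpoint.

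A reader might go further and infer that the SAP discards most cases of the device's commonest adverse event and so flatters VenaSeal. The documents do not support this:
- The ranking as most common comes from one 50-subject single-arm study. The other study summaries in section 4.1 do not rank adverse events.
- There is no grade split from which to derive a number lost.
- The direction is open. The same wording applies to every arm. ETA also closes the truncal vein, which is P2's stated cause, and P3's stated cause is not confined to the adhesive. In the stripping study, protocol section 10.9 allows branch phlebectomy at the index procedure for stripping but not for VenaSeal, so omitting P2 could favour VenaSeal. But stripping removes the treated vein, so a treated-vein definition could lower the comparator's count as well.

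**Conclusion.** The two definitions conflict, and the SAP's wording taken literally yields a narrower named phlebitis endpoint than the protocol's in all three studies. Subjects without a P1 component fall outside it, and non-allergic P3 reactions fall outside both the phlebitis and the hypersensitivity definitions. This rests on taking the SAP's printed definition and sorting rule at face value; the Charter could change the result in practice.

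The size cannot be determined. It runs from no effect, if every affected subject also has P1 or the CEC counts all grades, to a material understatement if isolated P2 or P3 is common. The direction of any between-arm effect is likewise unknown. No hypothesis test or type I error is affected. The matter is a descriptive safety result whose meaning is unsettled, and it is worth correcting before the safety tables are produced.

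**What to change.** In SAP 7.9.1.5 and 7.9.2.4, replace the phlebitis definition with the Appendix B P1/P2/P3 definition, and confirm that the CEC Charter uses the same one. If it does not, reconcile the three documents and state which governs.

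Report the number of subjects with any phlebitis and with each grade, by arm in the randomized studies and overall in the VLU Study. Note that a subject may appear under more than one grade. State how many P3 subjects are also counted under hypersensitivity, so that overlap and gaps are visible.

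The cost is a wording change in two SAP sections, a check of the Charter and one expanded table. The stated phlebitis rate may be higher than under the present wording.
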